4.2.3. Premature Withdrawal and Missing Data

All data collected in the study database after the subject’s cessation of study treatment should be included in summary and analysis. Data of subjects who withdraw after the screening examination or are not treated will only be listed. Assessments taken after the End of Study visit date for subjects continuing on to study URO-901-3006 will not be included in analysis or listings for study URO-901-3005; it will be included in datasets to support inclusion in analysis of study URO-901-3006.

If any visits are missing diary data, no explicit missing data imputation will be performed for the primary analysis of change from baseline since a mixed model for repeated measures (MMRM) will be applied to change from baseline analysis. If time to bed or time to awaken the next morning is missing from a diary day, the average of non-missing days for that subject at that visit

will be used. If no visit average bedtime or time of awakening is calculable, no nocturia measurements will be calculated for that subject at that visit.

Missing items from the subject reported outcomes (PROs) will be handled according to the respective measure instructions as described in Section 4.3.2.

Missing return dates from the study drug log will be imputed as the day of the subsequent drug dispensation, end of treatment visit, or subject discontinuation in the study, whichever is first. Non-return of IP will be considered taken per protocol for calculation of treatment compliance but will be noted in the listing of study medication.

If the first dose of double-blind study medication is not witnessed, the start of medication will be imputed as the day after the drug was dispensed.

In general, missing safety data will not be imputed and only observed values will be analyzed.

If the relationship of an AE record (“Relationship to investigational product” on AE CRF) is missing this AE will be considered “Probably Related” to the study treatment. If the AE intensity is missing every effort should be made to acquire the information from the investigator. “Severe” will be assigned to a missing intensity for reporting purposes.

The general imputation rules of partial missing date and time for both AE and concomitant medication is detailed below:

Dates missing the day of the year will adhere to the following conventions:

- The missing day of onset date will be set to:
 - First day of the month that the event occurred, if the onset YYYY-MM is after the YYYY-MM of first double-blind treatment
 - The day of the first double-blind study treatment, if the onset YYYY-MM is the same as YYYY-MM of the first double-blind treatment
 - The day of the first run-in treatment, if the onset YYYY-MM is the same as YYYY-MM of the first run-in treatment, but different from YYYY-MM of the first double-blind treatment
 - The date of informed consent, if the onset YYYY-MM is before the YYYY-MM of the first run-in treatment.
- The missing day of end date will be set to:
 - The death date, if the end date YYYY-MM is the same as the YYYY-MM of the death date
 - The end of study participation, if the end date YYYY-MM is the same as the YYYY-MM of the end of study participation date
 - The last day of the month of the occurrence otherwise.

Dates missing both the day and month of the year will adhere to the following conventions:

- Missing onset date will be set to:

- January 1 of the year of the onset, if the onset YYYY is after the YYYY of the first double-blind treatment
- The date of the first run-in treatment, if the onset YYYY is the same as YYYY of the first run-in treatment, but different from YYYY of the first double-blind treatment
- The date of the first double-blind treatment, if the onset YYYY is the same as YYYY of the first double-blind treatment
- The date of informed consent, if the onset YYYY is before YYYY of the first run-in treatment
- The missing end date will be set to:
 - The death date, if the end date YYYY is the same as the YYYY of the death date
 - The end of study participation, if the end date YYYY is the same as the YYYY of the end of study participation date
 - December 31 of the year of occurrence otherwise.

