5.1. Inclusion Criteria

At the **Visit 1 (Screening)** visit (and other timepoints as noted), a subject will be eligible for inclusion in this study only if all of the following criteria apply, unless otherwise noted:

1. Capable of giving written informed consent, which includes compliance with the requirements and restrictions listed in the consent form.
2. Male subjects of 45 years of age and above.
3. Body weight ≥ 50 kg (inclusive).
4. Subject should have been on and agree to continue to stay on a stable dose of BPH treatment with either a) alpha blocker monotherapy or b) alpha blocker + 5 ARI. Subjects on alpha blockers should have started their therapy at least 3 months prior to screening and be on a stable dose at the start of screening. Subjects on a 5-ARI should have started therapy at least 6 months prior to screening and be on a stable dose at screening.
5. Has a history of overactive bladder symptoms (frequency of ≥ 8 micturition episodes per day and urgency episodes of ≥ 3 per day with or without incontinence) while taking pharmacological therapy for at least 2 months to treat LUTS due to BPH.
6. Subject has an IPSS total score of ≥ 8 at Screening and Visit 3 (Baseline).
7. Subject has a prostate-specific antigen (PSA) level < 4 ng/mL, or if ≥ 4 ng/mL but ≤ 10 ng/mL, prostate cancer has been ruled out to the satisfaction of the investigator.
8. Subjects agrees to not participate in another interventional drug or device clinical trial during the study.
9. In the opinion of the investigator, is able and willing to comply with the requirements of the protocol, including completing study questionnaires and the Bladder Diary.
10. At Visit 2 (Run-in) and Visit 3 (Baseline) visits, subject must have both additional qualifications based on the 3-day Bladder Diary period: a) having an average of ≥ 8 but ≤ 20 micturition episodes per day over the 3-day diary period, and (b) having an average of ≥ 3 urgency episodes per day over the 3-day diary period.
11. Subject must have a post void residual (PVR) volume value of < 100 mL at Screening, Visit 2 (Run-In) and Visit 3 (Baseline).

12. At Visit 2 (Run-in) and Visit 3 (Baseline) visits, having at least 2 average nocturia episodes per night based on 3-day Bladder Diary at baseline. Nocturia is defined as waking to pass urine during the main sleep period.

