5.6.1. Prior Medication

Prior medications are defined as those medications taken prior to the first dose of double-blind treatment. The prior non-OAB and prior OAB medications will be summarized separately.

The following criterion will be used for selecting prior OAB medication:

Table 6: OAB Medication Selection

Class	Variable Selected	Selection
Anticholinergics	Preferred Term	darifenacin, fesoterodine, fesoterodine fumarate hyoscyamine, oxybutynin, oxybutynin hydrochloride, propantheline, solifenacin, solifenacin succinate, tolterodine, tolterodine l-tartrate, trospium, trospium chloride
Beta-3 adrenergic agonists	Preferred Term	mirabegron, vibegron, solabegron

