6.1.2.3. MMRM with Stratification Factors as Observed

If more than 7% of subjects are misstratified, the co-primary MMRM efficacy analysis will be repeated using stratification factors as calculated from the baseline diary (baseline average number of daily micturition episodes, baseline incontinence) and prior medications (alpha blocker use with or without 5-ARI).

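### The partial-date rule in SAP 4.2.3 can place an onset at first dose even when the recorded end date shows the event or drug had already stopped, and in one branch it makes an established BPH drug look new on Day 1

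*SAP*

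**What the plan says.** SAP 4.2.3 introduces one set of rules: "The general imputation rules of partial missing date and time for both AE and concomitant medication is detailed below". SAP 5.5 applies them to procedures as well.

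Two branches send a partial onset to the first double-blind dose:

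- Day missing, month matches: "The day of the first double-blind study treatment, if the onset YYYY-MM is the same as YYYY-MM of the first double-blind treatment".
- Day and month missing, year matches: "The date of the first double-blind treatment, if the onset YYYY is the same as YYYY of the first double-blind treatment".

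Onsets before the run-in month or year go elsewhere. In the year-only case, for example: "The date of informed consent, if the onset YYYY is before YYYY of the first run-in treatment".

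Neither first-dose branch mentions an end date. SAP 5.5, 5.6.2 and 7.1 point back to 4.2.3 and add no such check.

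The imputed dates then drive classification:

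- **AEs.** Table 2 assigns AEs by start date. Its footnote exempts a Day 1 onset whose relatedness is marked 'Not applicable'.
- **Medications.** Table 2 uses any overlap with a period. SAP 5.6.2 makes a drug concomitant if it starts on or after first dose. SAP 5.6.1 states: "Prior medications are defined as those medications taken prior to the first dose of double-blind treatment".
- **Strata.** SAP 6.1.2.3 takes the as-observed 5-ARI stratum from prior medications.
- **Eligibility.** Protocol 5.1, inclusion 4: "Subjects on a 5-ARI should have started therapy at least 6 months prior to screening". The minimum for alpha blockers is 3 months.

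**The concern.** Dating an onset of unknown timing to first dose is a sound conservative convention for AEs. It stops being conservative when the record itself shows that the event ended before dosing. The rule then overrides collected data and produces a start date later than the stop date, which would be visible in the AE listings. A resolved event from the placebo run-in is counted as treatment-emergent. If relatedness is missing, 4.2.3 sets it to 'Probably Related', and the event also enters the treatment-related tables.

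For medications the convention has less justification. A washed-out OAB drug can appear in the concomitant OAB table. A BPH drug that must have been in use for months can appear to start on Day 1, which resembles the new BPH start prohibited in protocol 10.6.

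**Working it through.** The plan gives no figure on this point, so the check applies the rule to example records and then asks how often each branch can be reached.

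**Worked records.** Assumed calendar: consent 16 Aug 2021, first run-in dose 6 Sep 2021, first double-blind dose 20 Sep 2021.

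| Record | Start recorded | End recorded | Imputed start | Result |
|---|---|---|---|---|
| a. AE | ??-Sep-2021 | 8 Sep 2021 | 20 Sep 2021 | Starts 12 days after its end; TEAE unless relatedness 'Not applicable' |
| b. Any drug | 2021 only | 15 Aug 2021 | 20 Sep 2021 | Starts after its end; concomitant (5.6.2 and Table 2), and also prior (Table 2) |
| c. 5-ARI | 2021 only | ongoing | 20 Sep 2021 | Concomitant; not prior under 5.6.1 or Table 2 |
| d. Alpha blocker | ??-Mar-2021 | ongoing | 16 Aug 2021 (consent) | Prior and concomitant |
| e. BPH drug | 2018 only | ongoing | 16 Aug 2021 (consent) | Prior and concomitant |

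Record b stays prior because Table 2 accepts an end date that falls before the prior period closes, and 15 Aug precedes 20 Sep. Record c fails every clause of the overlap rule: its imputed start equals the close of the prior period and it has no earlier end date.

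**Reach for AEs.** The share of pre-dose onsets that the rule moves to Day 1, if onsets are spread evenly over the period before dosing:

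- 14-day run-in only, day missing: mean of (1 − k/30.4) for k = 1 to 14, which is 1 − 7.5/30.4 = 0.753.
- 14-day run-in only, day and month missing: 1 − 7.5/365 = 0.979.
- Whole pre-dose window of 28 to 53 days, first doses uniform over the calendar: 52% down to 28% with the day missing, and 96% down to 93% with only the year known.

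These are shares of partial dates moved, not shares of false TEAEs. The clear errors are the subset with a recorded end before first dose and relatedness other than 'Not applicable'. The documents do not allow that subset to be counted.

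**Reach for BPH drugs.** A start at least 3 or 6 months before screening cannot share a calendar month with first dose, so the month branch is never reached (0 of 365 first-dose dates). The year branch can be reached only for first doses from about 11 April (alpha blocker) or 11 July (5-ARI), taking screening as late as 10 days before first dose.

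**Size for the 5-ARI stratum.** Inputs:

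- 5-ARI users: 544, half of 1088 (SAP 1.2.4.1).
- Share who started 7 to 12 months before first dose: 10% to 25% (assumed).
- Of those, share with a start in the calendar year of first dose: mean of (1 − d/12) for d from 7 to 12, which is 1 − 9.5/12 = 0.208.
- Share of start dates recorded as year only: 10% to 50% (assumed).

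Low: 544 × 0.10 × 0.208 × 0.10 = 1.1 men. High: 544 × 0.25 × 0.208 × 0.50 = 14.1 men. That is 0.1% to 1.3% of 1088. The trigger in 6.1.2.3 is more than 7%, or about 76 men (0.07 × 1088).

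**The case against.** The best defence is that first-dose imputation is a deliberate conservative choice, and that the plan contains limits which a quick reading misses. Much of this stands.

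- **Every moved AE is a false TEAE.** A reader might infer this, but the Table 2 footnote removes Day 1 events with relatedness 'Not applicable'. The protection is partial: protocol 10.3 asks the investigator to assess relationship for every AE, and a missing assessment becomes 'Probably Related'.
- **A washed-out anticholinergic disappears from prior use.** It does not. Its recorded end date keeps it prior under Table 2 (record b). The fault is that it is also counted as concomitant.
- **Established BPH drugs in general start on Day 1.** The effect needs both day and month missing and a start in the calendar year of first dose. Earlier years go to the consent date. That date also conflicts with the required duration of therapy, but the drug stays prior.
- **Alpha-blocker dates disturb the stratum.** Every eligible man takes an alpha blocker. Only the 5-ARI distinguishes the strata, so alpha-blocker dates do not belong in the size estimate.
- **The per-protocol set or the primary result changes.** Per-protocol exclusions are settled through the Protocol Deviation Plan and blinded review (SAP 3.1.7 and 3.2), and no programmed check on imputed dates is described. The primary MMRM and the subgroup models for the stratification factors use strata as randomized.

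It is also fair that 5.6.1 and 6.1.2.3 do not themselves cite the imputation rule, so the stratum could be derived from the medication record without imputed dates. The SAP does not say which, so the stratum effect is possible rather than certain.

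**Conclusion.** The point holds as a minor defect in wording. Read literally, SAP 4.2.3 can give an onset later than a recorded end date, make a resolved run-in AE treatment-emergent, and make a stopped drug or procedure concomitant. In the year-only branch it can also remove an ongoing BPH drug from prior use, against inclusion 4. No other section corrects this.

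The consequences are confined to the TEAE tables, the medication and procedure displays, and the as-observed stratum in a sensitivity analysis that runs only if more than 7% of men are misstratified. The figure of 1 to 14 men rests on unsourced shares for recent starts and year-only dates. Even at its upper end it could add to the 7% trigger but not reach it alone. The true number of affected records is unknown, because the documents give no count of partial dates.

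**What to change.** Add to SAP 4.2.3, for AEs, medications and procedures:

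1. The first-dose imputation applies only when the end date is missing or falls on or after the first double-blind dose.
2. Otherwise, impute the earliest date consistent with the recorded month or year (for AEs, not before informed consent), and never later than the recorded end date.
3. A BPH drug recorded as in use at Screening is classified as prior whatever its imputed start.

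Leave the convention unchanged for other onsets of unknown timing. A blanket first-of-month or 1 January rule for all medications would be worse, because a drug truly started after randomization could then look prior and a prohibited new start could be hidden.

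The cost is a few lines of SAP text and imputation code before lock, with slightly fewer conservatively assigned TEAEs and concomitant drugs. Some resolved run-in AEs may be dated before run-in rather than within it, which affects only the onset label in the listings.

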4.2.4. Assessment Windows

4.2.4.1. Study Reporting Periods

Based on study design and variables under consideration, study time periods are defined as below.

Table 2: Definition of Study Reporting Periods

Analysis description	Analyzing Study Period	Start Date	End Date
General	Screening	Date of informed consent	Date of first run-in dose
	Run-in	Date of first run-in single-blind dose	Date of last run-in single-blind dose
	Treatment (Day 1 – Week 24)	Date of first double-blind dose	Date of last double-blind dose + 5 days
	Follow-up (up to Week 27)	>Date of last dose + 5 days	Date of EOS visit
Adverse events (based on AE start date)	Prior	Date of informed consent	Date of first run-in dose
	Run-in	Date of first single-blind run-in dose	Date of first double-blind dose
	TEAE	Date of first double-blind dose*	Date of last dose + 5 days
	Post-Treatment	Date of last dose + 5 days	N/A
Concomitant Medication/Procedure (any overlap with period)	Prior medication/procedure	N/A	Date of first double-blind dose

Analysis description	Analyzing Study Period	Start Date	End Date
	Concomitant medication/ procedure	Date of first double-blind dose	Date of last double-blind dose + 5 days
	Post medication/ procedure	>Date of last double-blind dose + 5 days	N/A
EOS: End of study is defined as the date when the subject has completed one of the following: completes Week 24 Visit for subjects who enroll into Study URO-901-3006 or Safety Follow-up for subjects who do not enroll into Study URO-901-3006, discontinued from the study, or is lost to follow-up.			

*AEs with a start date equal to the date of first double-blind dose will be considered treatment-emergent unless the relatedness to study drug is marked 'Not applicable'.
 
Overlapping period: Medication start date<= period start date<medication end date, medication start date<period end date<=medication end date, or period start date<=medication start or end date<period end date, then the medication is considered overlapping with the period.
			

4.2.4.2. Analysis Visit Windows

Analysis visit windows for both diary and non-diary data are defined as shown in Table 3. All observations will be given an analysis visit, assigned based on relative study day, as defined in section 4.3.3. If fewer than three diary days are within the analysis window, only the data within the window will be used to calculate visit-level averages. Unless otherwise noted, all data will be listed.

Table 3: Analysis Window Slotting

Analysis window label	Nominal visit	Nominal day	Non-Diary Visit Window	Diary Visit Window
Screening	Visit 1	-49 to - 21	date of informed consent to date of first run-in dose	
Run-in	Visit 2	-14	date of first run-in dose to day -1	7 days prior to date of first run-in dose
Baseline	Visit 3	1	[-1,1]	date of first run-in dose to day -1
Week 1	Visit 4	8	[2, 11]	
Week 2	Visit 5	15	[12, 22]	[7, 18]
Week 4	Visit 6	29	[23, 42]	[19, 39]
Week 8	Visit 7	57	[43, 70]	[47, 67]
Week 12	Visit 8	85	[71, 98]*	[68, 102]
Week 16	Visit 9	113	[99, 126]	[103, 123]
Week 20	Visit 10	141	[127, 154]	[131, 151]

Analysis window label	Nominal visit	Nominal day	Non-Diary Visit Window	Diary Visit Window
Week 24	Visit 11	169	[155, last dose date + 5]	[159, 179]
Follow-Up for Early Withdrawals	NA	NA	>Last dose date + 5	
Follow-Up for Completers	NA	NA	>Last dose date + 5	

*Urodynamics window for Week 12 is [57, 113]

For subjects who withdraw early, assessments taken at the end of study visit will also be summarized with scheduled data if they fall within an on-study visit window and are within 21 days after the last treatment date.

For parameters which were **not** scheduled to be collected at all visits, still use the all-inclusive visit intervals defined for all visits (i.e., the window defined above) to slot records. However, if a value is slotted to a visit unscheduled for a parameter, it will not be summarized (and not be included in the efficacy datasets) but will be included in data listings.

1. If after all records have been slotted, there are multiple valid records within a visit, use the record by the following the rules below:
 - If there are more than three bladder diary days within the window, the three days closest to the nominal visit day will be used to calculate analysis visit averages. If two days are equidistant to the nominal visit day, the earlier day will be selected first.
 - If there are multiple values for other efficacy endpoints in one window, the visit closest to the nominal day will be selected for assessing endpoints at a particular visit and for by-visit displays. If the visits are equidistant from the nominal day, then the earlier visit will be selected. All values will be stored in analysis datasets.
 - The same visit windows will be used for safety and laboratory assessments. If there are multiple safety or laboratory values in one time window on-treatment, the worst value (furthest from the center of the normal range if both high and low abnormalities exist) will be selected for the by-visit analyses.

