7.1. Discontinuation of Study Drug

Subjects who discontinue study drug will complete the Week 24/Early Withdrawal assessments specified in the Schedule of Assessments ([Section 1.3](#) and [Section 1.4](#)).

Reasons for discontinuation from the study drug include the following:

- Any AE of urinary retention
- Any occurrence of PVR volume \geq 300 mL

Discontinuation of study drug for abnormal liver function should be considered by the investigator when a subject meets all of the conditions outlined in [Section 8.4.6.2](#) for Hy's law or if the investigator believes that it is in the best interest of the subject (reason for discontinuation will be AE).

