7.7. Uroflow Measures

Uroflowmetry is conducted at Screening and Week 24 (or early withdrawal). Measured parameters include maximum flow rate (Q_{max}) (mL/s), average flow rate (Q_{ave}) (mL/s), and volume voided (VV) (mL).

Uroflowmetry measures require a minimum void of 125 mL to be interpretable. Summary statistics will only be provided for uroflow tests where $VV \geq 125$ mL. The summary will comprise a continuous summary at baseline and post-baseline, including change from baseline. Least squares mean estimates and 95% CIs as described in section 4.2.2 will be presented from an ANCOVA model including terms for treatment and baseline parameter value.

If a uroflow measurement was taken after the end of study date in URO-901-3005 (implying that the subject initiated URO-901-3006 before the evaluation), that measurement will not be included in any tabular summaries but will be listed. All Uroflow measurements will be listed.

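### SAP 4.2.4.2 and 7.7 conflict on early-withdrawal uroflow: read literally, the visit-slotting rule leaves exit Qmax on Days 2 to 154 out of the uroflow summary and ANCOVA.

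*SAP*

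**What the plan says.** **Slotting rule (SAP 4.2.4.2).** The basis is study day: "All observations will be given an analysis visit, assigned based on relative study day". The same windows serve safety and laboratory data. The Week 24 non-diary window in Table 3 is "155, last dose date + 5". For parameters not collected at every visit, "if a value is slotted to a visit unscheduled for a parameter, it will not be summarized (and not be included in the efficacy datasets"; such values go to the listings.

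**Early-withdrawal sentence (same section).** When a man leaves before completing, "assessments taken at the end of study visit will also be summarized with scheduled data if they fall within an on-study visit window"; a second condition is that they lie within 21 days of his last treatment.

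**Uroflow section (SAP 7.7).** "Uroflowmetry is conducted at Screening and Week 24 (or early withdrawal". The analysis is then described as follows: "The summary will comprise a continuous summary at baseline and post-baseline, including change from baseline", with an ANCOVA as in SAP 4.2.2. Two exclusions from the summaries are stated: voided volume under 125 mL, and measurement after the end-of-study date.

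**Data after stopping treatment (SAP 4.2.3).** Data collected after treatment stops should be included in summaries and analyses.

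**Who has an exit uroflow (protocol 7.1, 7.2 and 10.7.10).** Urinary retention and a PVR of 300 mL or more are reasons for stopping study drug, and stopping drug means leaving the study. "Subjects who discontinue study drug will complete the Week 24/Early Withdrawal assessments specified in the Schedule of Assessments", and that visit includes uroflowmetry.

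**The concern.** Uroflow is a named safety endpoint, and the protocol gives urinary retention as a particular risk in this population. Urodynamic Qmax is measured in only about 60 men, so uroflowmetry is the only flow measure planned for the whole trial, and it has one post-baseline occasion.

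If exit values before Day 155 are dropped, the men left out are not a random subset. Those stopped for retention or high PVR leave because of the function that Qmax measures. If vibegron lowered flow in a minority who then stopped, the summary and ANCOVA would compare mainly men who had not run into voiding trouble, and the difference could be biased toward no effect. Because the SAP supports two datasets, two competent programmers could produce different uroflow tables from it.

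**Working it through.** **1. Which days lose the value under the literal rule.** Inputs are the non-diary windows in SAP Table 3 and the two schedules of assessments (protocol 1.3 and 1.4). After baseline, both schedules place uroflow only at Visit 11 or Early Withdrawal.

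| Window | Days | Number of days | Uroflow scheduled at that week? |
|---|---|---|---|
| Week 1 | 2–11 | 10 | no |
| Week 2 | 12–22 | 11 | no |
| Week 4 | 23–42 | 20 | no |
| Week 8 | 43–70 | 28 | no |
| Week 12 | 71–98 | 28 | no |
| Week 16 | 99–126 | 28 | no |
| Week 20 | 127–154 | 28 | no |
| Week 24 | 155 to last dose + 5 | – | yes |

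10 + 11 + 20 + 28 + 28 + 28 + 28 = 153 days, with no gaps or overlaps from Day 2 to Day 154. For example, an exit uroflow on Day 60 is slotted to Week 8, where uroflow is not scheduled, so it is only listed. Day 155 is the first day on which the value is summarised.

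**2. The same value under the other text.** SAP 7.7 treats early withdrawal as a planned uroflow time and names no week for the post-baseline summary. On that reading the Day 60 value is included, subject to the 125 mL and end-of-study exclusions. The early-withdrawal sentence in 4.2.4.2 also points to inclusion, but only alongside scheduled data, and Week 8 has no scheduled uroflow for it to join. SAP 4.2.3 favours inclusion without saying under which visit. The ANCOVA in SAP 4.2.2 is fitted separately for each timepoint, so which timepoint the value belongs to decides whether it enters the model.

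**3. How many men.** The plan's own figure comes first (protocol 9.2). With 1088 randomised and 15% assumed to discontinue before Week 12, 1088 × 0.85 = 924.8, against a stated 924. The corresponding loss is 0.15 × 1088 = 163.2, about 163 men (1088 − 924 = 164 with the plan's rounding). Men leaving between Week 12 and Day 154 would add to this; no rate is given for them.

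The 163 limits the men affected before Week 12 under the planning assumption. It does not count uroflows lost, for two reasons:
- Protocol 7.2 asks for exit assessments only where they can be done, and reasons for leaving include loss to follow-up, withdrawn consent and death.
- Voids under 125 mL are excluded whichever rule applies.

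The number stopped for retention or PVR is not given, so the bias in Qmax cannot be computed.

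**4. IPSS.** The same rule reaches exit IPSS scores slotted to Week 1 or Week 2, and to Week 16 in Part 2, where IPSS is not scheduled.

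**The case against.** The strongest reply is that SAP 7.7 is the section specific to uroflow and already settles the matter. It names early withdrawal, uses an open post-baseline category where PVR (7.5) and IPSS (7.8) are summarised by visit, and lists its own exclusions, none of which is study day. An exit uroflow is then arguably not an unscheduled value at all.

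This has force, and it is why exclusion cannot be treated as the settled plan. It does not close the question. Section 7.7 contains no exemption from slotting, whereas the SAP writes such exceptions out elsewhere: a separate Week 12 window for urodynamics, an any-time post-baseline category in 7.6, and maximum and last post-baseline rows for vital signs.

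Two further replies stand:
- **The 125 mL filter.** A retention event as defined in protocol 8.4.6 requires catheterisation. Some of these men may not void 125 mL, so their exit Qmax would be excluded anyway and the proposed wording would not recover it.
- **Other voiding outputs.** PVR is summarised at every visit and by category up to 300 mL or more, urinary retention is an adverse event of special interest, events leading to discontinuation are tabulated, and all uroflow data are listed. A reader might infer that the retention signal disappears from the report; the documents do not support that.

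**Conclusion.** The conflict is real and should be resolved before unblinding, so that the choice cannot depend on results. One stated rule, applied as written, removes every exit Qmax on Days 2 to 154 from the summary and ANCOVA; other text points to keeping it; no order of precedence is given. The possible bias toward no effect depends on the literal rule being applied and on some men with reduced flow leaving before Day 155 with an interpretable void.

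Two stronger readings are tempting and go too far. A reader might infer that the uroflow analysis covers only men who completed. Even under the literal rule, a man who withdraws on or after Day 155 is summarised if measured within 5 days of his last dose. A reader might also take 163 as the number of uroflows discarded; it is a planning ceiling on all-cause departures before Week 12.

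The point concerns a selected safety comparison of unknown size, with the main voiding-safety information preserved elsewhere. It merits correction but does not threaten the trial's conclusions on retention.

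**What to change.** **Uroflow.** State in SAP 4.2.4.2 and 7.7 that the post-baseline uroflow summary and ANCOVA use the Week 24 or early-withdrawal value whatever its study day, keeping the 125 mL and end-of-study exclusions. Say whether the 21-day limit in 4.2.4.2 also applies. Show values from Day 155 onward separately.

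**IPSS.** Add a last post-baseline row in SAP 7.8, so that exit scores slotted to Week 1, Week 2 or (Part 2) Week 16 are not lost.

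**Cost.** SAP wording and an extra row in the affected tables; the data are already collected. The small downside is that the pooled uroflow timepoint mixes durations of exposure, which the separate Day 155+ display makes visible.
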